25.2 General Analytic Issues

Missing Data. We will first test if the data are missing at random by forming a dummy variable that indicates the presence or absence of missing data on a variable. If the data are missing at random, the correlations with other variables should be trivial. We will use the EM method as implemented in SOLAS or FIML in Amos to impute missing data. If the data are not missing at random, then we will include dummy variables that explicitly model the nature of the missing data.

Outlier Analysis and Response Distributions. Throughout all of our statistical analyses, we will be sensitive to the potential influence of outlier cases and possible biases due to ill-behaved (i.e., nonnormal) distributions. Where necessary, we will use robust analytic techniques. Measurement Error. Many of our variables will be subject to some measurement error that, in turn, can bias our parameter estimates. Where possible, we will pursue analytic strategies that permit us to incorporate an error theory into our parameter estimation methods (structural equation modeling). When multiple indicators of an underlying latent variable are present, the incorporation of an error theory is straightforward. When an error theory cannot be empirically operationalized, we will take care to interpret our data in light of the potential bias that may be present.

Multiple Tests and Evaluation of Study Aims. Some of our analyses will have multiple DVs. We will be sensitive to inflated experiment-wise error and control it with the multivariate F statistic based on Pillais criterion in our MANOVAs or with modified Bonferroni methods based on recommendations of Jaccard, [name], and Kirk.

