- 6) 1-month and 3-month follow-up surveys will be conducted online to reduce burden and allow participants to complete them from home. Participants can request mailed, paper-based surveys if they do not want to complete the online version of the survey. Paper-based cover letter and surveys will be mailed to participants' homes along with prepaid return envelopes. Both the online version of the follow-up surveys as well as the hardcopy surveys (which will include identical questions/prompts as the REDCap survey), will include the text at the beginning of the survey that states "By completing the following survey you are agreeing to take part in this research study. If you have any questions about the survey or your participation, please contact project coordinator, [name], at [contact] or [contact]". Participants will receive an invitation email, up to 5 reminder emails, and up to 3 reminder phone call attempts to complete each survey. During the baseline survey, participants will also be asked if they would like to receive SMS text message reminders to participate in the follow-up surveys. If participants opt into receiving SMS text message reminders, they will receive 2 text message reminders for each survey along with all other contact methods.

Subjects will be informed in the consent process:

"You should be aware that it is illegal in the Commonwealth of Pennsylvania to text while driving. It is also dangerous to pay attention to your cellular phone while driving, walking, or doing any activity that requires your attention. You should continue to exercise good judgment on this while participating in this study."

Please note: Mailed hardcopy surveys/letters will only be offered to individuals who indicate that they do not have access to the internet, not as an option for all participants. With the timeframe between the 1-month survey and the 3-month survey being shorter, we do not want there to be any overlap of surveys if participants are slow to mail back their responses.

Recruitment of Physician Interventionists:

- The dermatologists from the intervention site will undergo 1 session of training to deliver the ABC intervention, following the same protocol developed and used in the R03 study. A weekly scheduled journal club meeting will be cancelled and this training will take the place of it in the evening (instead of morning) and will require no additional time commitment from the dermatologists to participate in the training or study.

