9.0 Statistical Plan

9.1 Sample size determination

874 is the maximum number of patient participants to be enrolled. The number of participants that will be contacted (874) is much larger than the number we intend to enroll (227). Based on the response rate of the first cohort in Spring 2016, we are confident that the recruitment process explained above will yield the required number of participants within the proposed period.

27 participants were enrolled during the first cohort in 2016.

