25.3 Aim 1: Evaluate efficacy of the ABC intervention

[name] (Co-I) will conduct all outcome analyses in order to avoid any bias. First a 2 (Group: ABC vs. Controls) x 3 (Time: baseline, 3 & 6 mo. follow-up) Mixed ANOVA will be conducted to test the intervention on a given outcome variable (e.g., use of sun protection). First, we expect to observe a main effect of Group with the highest reports of sun protection (and lowest reports of UV risk behaviors) occurring in our ABC condition. Second, we anticipate observing a Group x Time interaction with no differences between the groups at baseline but differences (lower risk in the ABC group) at each of the follow-ups. He will also assess the scientific and clinical significance of the effects utilizing the magnitude estimation approach described by Jaccard. Specifically, statistical significance refers to the case when the null hypothesis is rejected, whereas magnitude estimation approaches emphasize the size of the effect. To utilize magnitude

estimation approaches, the researcher must specify an a priori effect size that differentiates a trivial effect from a meaningful effect. If the effect size observed is less than the criterion for meaningfulness, then the result is deemed nonsignificant, even if the null is rejected. We will use Cohen's d statistic to assess clinical significance of the main effects and interactions. We will define an effect as clinically and statistically significant to the extent that the d is greater than or equal to .20.

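### The SAP tests for missing at random with a criterion for missing completely at random, and lets the answer trigger an undefined dummy-variable step

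*Combined protocol and SAP*

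**What the plan says.** The Missing Data paragraph of SAP section 25.2 sets out three steps.

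- **The test.** "We will first test if the data are missing at random by forming a dummy variable" for presence or absence of a value. The criterion is "If the data are missing at random, the correlations with other variables should be trivial". There is no cut-off for trivial, no significance level and no list of variables to be screened.
- **The default.** "We will use the EM method as implemented in SOLAS or FIML in Amos to impute missing data". This carries no condition, so it appears to apply whatever the test shows. How imputation uncertainty reaches the Aim 1 standard errors is not stated.
- **The branch.** "If the data are not missing at random, then we will include dummy variables that explicitly model the nature of the missing data". The plan does not say into which model the dummies go, whether they interact with time or group, or how results are averaged over them.

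The analysis affected is the 2 x 3 Mixed ANOVA in section 25.3, which looks at both Group ("First, we expect to observe a main effect of Group") and Group x Time. That section adds an effect-size filter at d = .20: "If the effect size observed is less than the criterion for meaningfulness, then the result is deemed nonsignificant, even if the null is rejected".

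**The concern.** Under MCAR, missingness is unrelated to anything measured, so the dummy correlations should be near zero. MAR is weaker: missingness may depend, even strongly, on observed data, and likelihood methods such as FIML remain valid. Under MNAR, missingness depends on the unseen value itself, and whether it shows up in observed correlations depends on how closely that value tracks what was measured. The stated criterion is therefore the MCAR one under the wrong name.

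This is more than terminology, because the label drives the analysis. A failed check adds a model step for dropout that EM or FIML already handles, and the analyst has to invent that step after seeing the data. A pass gives no protection against MNAR. Conditioning on dropout dummies is not a general remedy for MNAR, and it can move the group contrasts when dropout differs by arm. That is possible here: the arms are two different clinics without randomization (section 7.1).

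**Working it through.** **Inputs.** N = 227 is the planned enrolment (section 9.1: "is much larger than the number we intend to enroll (227"). The d = .20 filter is from section 25.3. The documents give no dropout rate, dropout slope or correlation over time, so these are assumed: dropout p of 10%, 20% or 30%; slope b of 0.3, 0.5 or 0.8 log-odds per SD; correlation rho between time points of 0.3, 0.5 or 0.7. Section 25.2 states no figure to reproduce.

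**(a) True MAR: dropout depends on baseline only.** To first order the dummy-baseline correlation is r = b x sqrt(p(1 - p)). At p = 0.20 this is b x 0.40, or 0.12, 0.20 and 0.32. With 227 patients, p < .05 needs |r| > 1.97/sqrt(225 + 1.97^2) = 0.130. By Fisher's z the chance of a flag is Phi((atanh r - 0.131) x sqrt(224)). For r = 0.12 this is Phi((0.1206 - 0.1310) x 14.97) = Phi(-0.16), about 44%. Simulation (4,000 data sets per cell) gave:

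| Dropout | Rule | b = 0.3 | b = 0.5 | b = 0.8 |
|---|---|---|---|---|
| 10% | p < .05 | 27% | 59% | 92% |
| 20% | p < .05 | 44% | 83% | 99.7% |
| 30% | p < .05 | 53% | 92% | 100% |
| 20% | abs(r) >= .10 | 61% | 92% | 99.9% |
| 20% | abs(r) >= .20 | 10% | 47% | 92% |

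Every flag here is a wrong label. At b = 0.5 and 20% dropout, the choice of an unstated cut-off moves the rate from 47% to 92%. Under true MCAR a single correlation still reaches 0.10 in 14% of data sets.

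**(b) True MNAR: dropout depends on the unseen follow-up value, b = 0.5, p = 0.20.** The dummy now relates to baseline only through rho, so r is about 0.20 x rho: 0.06, 0.10 and 0.14. Share passed as MAR:

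| Rule | rho = .3 | rho = .5 | rho = .7 |
|---|---|---|---|
| p < .05 | 86% | 70% | 47% |
| abs(r) < .10 | 72% | 51% | 29% |

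**(c) Effect of the dummies in EM-filled data: MAR dropout, rho = 0.5, no true effect, both follow-ups lost together.** Dropouts differ from completers by about b SD at baseline, so by (1 - rho)b in expected change and by b(1 + 2 rho)/3 in the mean over three time points. Adjusting for the dummy moves the group contrast by that amount times the difference in dropout between clinics.

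- Group x Time, dummy x time: at 15% v 25%, 0.10 x 0.5 x b = 0.015 to 0.04 SD (simulated 0.01 to 0.04, including unweighted pattern means). At 10% v 30%, 0.20 x 0.5 x b = 0.03 to 0.08 SD (simulated 0.03 to 0.08).
- Group, dummy as main effect only: 0.10 x (2/3) x b = 0.02 to 0.05 SD (simulated 0.02 to 0.05), and 0.20 x (2/3) x b = 0.04 to 0.11 SD (simulated 0.04 to 0.10). Group x Time does not move in this mode, because the dummy is constant within a patient.
- Equal dropout: no bias in any mode. Weighting by each arm's own pattern proportions, or FIML without dummies: 0.00.

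**(d) Conditional: one EM-filled data set analysed as if observed, rho .3 to .7, b = 0.5, no true effect.** The filled values are then counted as real data. Simulated type I error for Group x Time:

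| Missing | p < .05 alone | and abs(d) >= .20 |
|---|---|---|
| 10% | 8-10% | 3-5% |
| 20% | 12-14% | 3-7% |
| 30% | 18-21% | 4-10% |

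An observed-data likelihood model gave 4-6% and 2-4%. The SAP does not define d for an interaction; here it is mean follow-up minus baseline, in baseline SDs.

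**The case against.** The best defence is that the authors used the term loosely and meant MCAR. The check is then coherent, and the unconditional EM/FIML default already deals with baseline-related dropout. A wrong label on its own biases nothing: harm needs a flag, unequal dropout between clinics and an unfavourable way of entering the dummies. Even then the largest shift is half the .20 threshold and, against an estimator SD of about 0.11 to 0.13, at most about 0.9 standard errors. Retention effort is substantial ("Participants will receive an invitation email, up to 5 reminder emails, and up to 3 reminder phone call attempts to complete each survey"), and nothing in the documents predicts unequal loss. A single EM fill is not stated, FIML is a named alternative, and the .20 filter removes much of the inflation in (d). Finally, replacing the test does not cure MNAR.

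Most of this stands as a limit on size. Part (d) is conditional, and (b) shows only that a pass should not reassure. In a separate simulation with slope 0.7, MNAR dropout running in opposite directions in the two arms moved the MAR likelihood estimate from 0.20 to between -0.01 and -0.17, and the check flagged it no more often than MCAR. What does not stand is the claim that only wording is at fault. Renaming the test leaves a branch that adds unspecified dummies to data that EM or FIML already handles.

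**Conclusion.** The concern holds. The criterion in section 25.2 is for MCAR, not MAR; this needs no assumption about dropout. How often the label is wrong does depend on the assumed rates, slopes and cut-off, but it is common over most of the range examined. The bias that follows is small and conditional: none with equal dropout, 0.01 to 0.05 SD at 15% v 25%, and up to about 0.08 SD (Group x Time) or 0.10 SD (Group) at 10% v 30%, in some modes of entry only. The inflation of type I error applies only if a single EM-filled data set is analysed as observed. This should be corrected, because the branch adds risk and analyst discretion with no compensating gain. It does not by itself undermine the study.

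**What to change.** In section 25.2:

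1. Delete the test of missing at random and the dummy-variable branch.
2. State that Aim 1 will be analysed, whatever the dummy correlations show, by FIML or a likelihood mixed model (group, time, group x time) on all observed data, or by multiple imputation with group in the imputation model and Rubin's rules. Use observed predictors of missingness as auxiliary variables.
3. Keep the dummy correlations as a descriptive check for departure from MCAR and as a guide to auxiliary variables. Report missingness by clinic.
4. State that a single EM-filled data set will not be analysed as if observed.
5. Optionally, add an MNAR sensitivity analysis, since no check on observed data can rule MNAR out.

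The cost is a few sentences and a little more analysis. FIML is already in the plan, and data collection does not change. Intervals will be slightly wider than after a single EM fill, as they should be.

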25.3 Aim 1: Evaluate efficacy of the ABC intervention

[name] (Co-I) will conduct all outcome analyses in order to avoid any bias. First a 2 (Group: ABC vs. Controls) x 3 (Time: baseline, 3 & 6 mo. follow-up) Mixed ANOVA will be conducted to test the intervention on a given outcome variable (e.g., use of sun protection). First, we expect to observe a main effect of Group with the highest reports of sun protection (and lowest reports of UV risk behaviors) occurring in our ABC condition. Second, we anticipate observing a Group x Time interaction with no differences between the groups at baseline but differences (lower risk in the ABC group) at each of the follow-ups. He will also assess the scientific and clinical significance of the effects utilizing the magnitude estimation approach described by Jaccard. Specifically, statistical significance refers to the case when the null hypothesis is rejected, whereas magnitude estimation approaches emphasize the size of the effect. To utilize magnitude

estimation approaches, the researcher must specify an a priori effect size that differentiates a trivial effect from a meaningful effect. If the effect size observed is less than the criterion for meaningfulness, then the result is deemed nonsignificant, even if the null is rejected. We will use Cohen's d statistic to assess clinical significance of the main effects and interactions. We will define an effect as clinically and statistically significant to the extent that the d is greater than or equal to .20.

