3.0 Inclusion and Exclusion Criteria

3.1 Inclusion Criteria

Patients must be:

- 1) Fluent in English
- 2) Mentally capable of giving consent and free of cognitive impairment (e.g., stroke, dementia, etc.)
- 3) Age 21-65 years old
- 4) A patient at Penn State Medical Center Dermatology Clinic in Hershey, PA or State College, PA, scheduled for a skin examination (either annual full body skin check or suspicious lesion) or scheduled for a Mohs surgical procedure.
- 5) Patients may include anyone who meets inclusion criteria (including previous skin cancer patients, newly diagnosed skin cancer patients, non-skin cancer patients)

Providers must:

- 1) Provide skin examinations (either annual full body skin check or suspicious lesion) or Mohs surgical procedures directly to patients (rather than supervise residents)
- 2) Treat patients that meet inclusion criteria for the study

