- 3) For those who are called and invited to participate over the phone by a PSHMC research assistant, the research assistant will explain the study, and if the patient is interested, the research assistant will obtain verbal consent to screen patients to see if they qualify for the study based on the inclusion/exclusion criteria. If they are eligible, they will then be formally invited. Potential participants interested in the study will be asked to arrive 25 minutes early for their appointment so that the consent form may be reviewed with them in its entirety and signed informed consent can be obtained in a private area of the clinic prior to the completion of the brief baseline survey. A log will be kept of all de-identified patients contacted via phone who declined participate when approached in the clinic (example: adult male #1 refused study due to time commitment).
- 4) In the first cohort in Spring 2016, we enrolled 27 participants who qualified after completing the screening. For the second cohort in Spring 2017, we plan to enroll an additional sample of 200 (100 per site). Based on the response rate of the first cohort in Spring 2016, we will invite up to 770 participants in Spring 2017. Once the target enrollment of 200 total (about 100 per site) is obtained, we will discontinue recruiting. The study will be split into 2 cohorts

– one taking place in Spring 2016 (n=27) and the other taking place in Spring 2017 (target n=200).

- 5) Participants who are interested and who qualify to participate will either: 1) be asked on the phone for their email address in order to send a copy of the consent form and reminder to arrive at their scheduled appointment 25 minutes prior to their scheduled time, or 2) receive a copy of the informed consent and a letter by mail reminding them to arrive at their scheduled appointment 25 minutes before their scheduled time to perform the written informed consent process and to complete the baseline survey. Participants will also be called 1-3 days before their scheduled appointment to remind them to arrive 25 minutes early (see reminder phone script).

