6.3 Waiver or alteration of authorization statements of agreement Not Applicable

7.0 Study Design and Procedures

7.1 Study Design

This study will use a longitudinal design to compare the effect of the ABC intervention on the intervention group versus the control group receiving TAU. Participants will not be randomized to a group. Instead, patients who meet eligibility criteria at PSHMC will be invited to participate at the intervention site, and current patients who meet eligibility criteria at the clinic in State College will be invited to participate at the control site.

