7.2 Study Procedures

Subjects will be recruited from two sites: 1) Penn State Hershey Medical Center Clinic in Hershey (PSHMC), which will serve as the intervention site where patient participants will receive the ABC interventions, and 2) Penn State Medical Group in State College (State College), which will serve as the control site where patient participants will receive TAU.

- 1) Participation will begin when participants are screened for eligibility over the phone.
- 2) Participation will continue for subjects when they arrive at either PSHMC or State College for an appointment with a participating physician that will include a skin check (either annual full body skin check or suspicious lesion) or Mohs surgical procedure (please see the recruitment section for a step-by-step process of how eligible participants will be obtained). A skin check involves the physician checking the patients' skin for any growth or mark that could potentially become cancerous. Patients at the control site will be receiving TAU for their skin check; patients at the intervention site will receive a normal skin-check, combined with the ABC-intervention (see uploaded information sheet). The audio recordings which will be done at both the control and intervention sites for all participants will be used to compare the information patients receive from their doctor during the course of a skin check.
- 3) Participants will be asked to arrive 25 minutes prior to their appointment so the informed consent process may take place prior to any study related procedures being conducted. After they check in, they will be greeted by a research assistant in the waiting room and directed to a private area within the clinic. The research assistant will be accessible while the participant completes the survey to answer questions that may arise. The baseline survey will assess demographic information, history of skin cancer, UV risk behaviors, perceived risk of skin cancer, dermatologist communication, attitudes about sun protection behavior, self-efficacy about sun protective behaviors, etc. (Please refer to Measures document for full questionnaire).

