16.0 Number of Subjects

The total maximum number of participants to be enrolled is 894.

The number of patient participants that will be contacted (up to 874) is much larger than the number we intend to enroll (227 – including both Cohort 1 and Cohort 2) (27 enrolled in Cohort 1 between Intervention and Control; 200 intended to enroll in Cohort 2 – 100 intervention, and 100 control). Based on the response rate of the first cohort in Spring 2016, we anticipate a 26% overall response rate, resulting in 200 individuals (for cohort 2) who agree to participate. However, due to uncertainty on the

overall response rate, participants will be invited in chunks and once we hit our target enrollment, we will stop recruiting. Additionally, we will enroll up to 20 providers (up to 10 from the control site and up to 10 from the intervention site).

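### Aim 1 compares two non-randomised clinics with an unadjusted 2 x 3 mixed ANOVA, so case-mix differences can bias the Group main effect and, under narrower conditions, Group x Time

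*Combined protocol and SAP*

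**What the plan says.** Protocol section 7.1 is explicit about allocation: "Participants will not be randomized to a group". Hershey patients form the ABC arm, and "current patients who meet eligibility criteria at the clinic in State College will be invited to participate at the control site". Arm and clinic are therefore the same variable.

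The eligibility criteria (3.1) admit a wide mix at both clinics, "including previous skin cancer patients, newly diagnosed skin cancer patients, non-skin cancer patients", attending for a skin check or for Mohs surgery. Nothing requires the mix to be alike.

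Several likely prognostic factors are recorded before the visit (7.2): "The baseline survey will assess demographic information, history of skin cancer, UV risk behaviors, perceived risk of skin cancer, dermatologist communication".

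For Aim 1, SAP section 25.3 states: "First a 2 (Group: ABC vs. Controls) x 3 (Time: baseline, 3 & 6 mo. follow-up) Mixed ANOVA will be conducted". It expects, first, a Group main effect favouring ABC and, second, a Group x Time interaction in which the groups are alike at baseline and separate later. It treats d of at least .20 as the mark of a meaningful effect. Neither section 9.2 nor sections 25.1 to 25.3 name a covariate, matching, propensity or cohort term for Aim 1. Regression appears in 9.2 for preliminary work and, in moderated form, for Aim 2.

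Gender, age and skin-cancer history appear in 1.3 as moderators for Aim 2. Section 25.4 adds each qualitative moderator to the ANOVA in a separate analysis.

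**The concern.** Without randomisation, similar groups are a hope rather than a property of the design. Section 25.3 anticipates no baseline difference but does nothing to secure it and gives no step to take if it fails.

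The two terms that the plan reads as efficacy are exposed to different degrees:

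- **Group main effect.** It averages over all three waves, baseline included. Any factor that differs between clinics and predicts the level of sun protection shifts it, even if nothing changes over time.
- **Group x Time.** Stable differences between clinics cancel. What remains is any factor that differs between clinics and also predicts how behaviour moves after the visit. A newly diagnosed or Mohs patient, for example, might change habits more than an annual-check patient whatever the dermatologist says.

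The target effect is small, so modest case-mix differences could account for a sizeable part of it. The data to remove the measured part are already being collected.

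**Working it through.** The plan gives no figure for confounding to reproduce. Its only Aim 1 design figure, power above 0.90 in 25.1, does not bear on this point. The yardstick used here is the plan's own d = .20.

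**Inputs from the documents.** Intended enrolment is 227 (sections 9.1 and 16.0), or about 113 per arm. There are two groups and three waves (25.3).

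**Assumed inputs.** Correlation between waves .5, two-sided alpha .05, outcome SD 1, true ABC effect zero, one binary covariate. The imbalances and effects below are illustrations; the documents give none.

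**1. Bias in Group x Time.** Bias = (difference in covariate share between clinics) x (covariate's extra change from baseline).

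- Setting A: (0.50 − 0.30) x 0.3 = 0.06 SD, which is 0.06/0.20 = 30% of the threshold.
- Setting B: (0.60 − 0.30) x 0.5 = 0.15 SD, which is 75% of it.
- Wider range: 0.1 x 0.1 = 0.01 SD, negligible, up to 0.5 x 0.5 = 0.25 SD, above the threshold.

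**2. False-positive rate of the planned test.** Group x Time in a 2 x 3 design has 2 degrees of freedom. With a spurious group difference of 0, b, b over the waves, the noncentrality is (n/2) x (2b²/3)/(1 − correlation).

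- Setting A: 56.5 x 0.0024/0.5 = 0.27, about 7% rejection.
- Setting B: 56.5 x 0.015/0.5 = 1.70, just under 20%. Simulation, which also counts the covariate's variance within clinics, gives about 19%.

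A single contrast of mean follow-up minus baseline rejects in about 8% and 24%, but that is not the test the plan names. With the covariate added to the model for that contrast, rejection returns to about 5% in both settings.

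**3. Bias in the Group main effect.** Bias = (difference in share) x (covariate's effect on level). Here the covariate shifts level by 0.5 SD and does not affect change (simulation, N = 200, wave correlation .6).

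| Share by clinic | Main-effect bias | Main-effect rejection | Group x Time bias |
|---|---|---|---|
| 50% vs 30% | 0.2 x 0.5 = 0.10 SD | 11.6% | 0 |
| 60% vs 20% | 0.4 x 0.5 = 0.20 SD | 35.5% | 0 |

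The main effect is thus the more exposed term: it needs no link between the covariate and change.

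**4. Cohort year.** The 2016 cohort is 27 of 227 (12%), and section 16.0 says only "27 enrolled in Cohort 1 between Intervention and Control". Split 14 and 13, with 100 per arm in 2017, the shares are 14/114 and 13/113, a difference of 0.008. Even a 0.5 SD difference between cohorts in change then gives a bias of 0.004 SD. If all 27 were in one arm, it would be (27/127) x 0.5 = 0.11 SD, but section 16.0 describes enrolment in both arms.

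**5. Form of adjustment.** A covariate entered only as a main effect shifts all waves equally and leaves Group x Time essentially unchanged. It has to enter with its interaction with Time, or in a model for change.

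**The case against.** The best reply is that the plan does not wholly ignore these factors. A group x time x gender ANOVA, as 25.4 describes, contains gender x Time, so its Group x Time effect already allows for gender; the same holds for each qualitative moderator in turn. That stands, and it narrows the gap. What remains is that these models serve Aim 2, take one factor at a time, and are nowhere named as the source of the Aim 1 estimate.

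A reader might infer that naming gender, age and cancer history as moderators concedes that they confound Group x Time. It does not. Moderation means that the effect of ABC differs between subgroups. Confounding of Group x Time needs a difference in trend that would exist without ABC, and no section asserts one.

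A reader might also infer that the clinics are known to differ, or that the result will be biased. The documents report no imbalance, and the settings above are assumptions. Nor is cohort year a strong confounder: its effect is negligible unless the 27 were split very unevenly.

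Finally, section 1.1 calls the study a preliminary analysis ahead of a large randomised trial, and adjustment cannot repair a design in which arm equals clinic. Both points are fair and bear on severity. They do not remove the case for using data already in hand.

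**Conclusion.** The point holds in this form. The Aim 1 analysis is an unadjusted comparison of two non-randomised clinics. Its Group main effect is open to bias from any imbalanced predictor of outcome level, and its Group x Time effect to bias from an imbalanced predictor of change. Under the assumed settings the Group x Time bias is 0.06 to 0.15 SD against a threshold of .20, with false-positive rates of about 7% and 19% for the planned test. Smaller imbalances would make it negligible.

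The size rests entirely on assumed imbalances, effects and wave correlation; the exposure rests on the text. Given the study's preliminary purpose, the one-at-a-time coverage in 25.4 and the absence of any documented imbalance, this is something the plan should fix rather than a fatal defect. The conflict between the follow-up times in 25.3 and those in sections 4.2 and 7.2 is a separate matter and does not affect it.

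**What to change.** In section 25.3:

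- Pre-specify, as the Aim 1 estimate, the Group x Time effect from a longitudinal model with Group, Time, Group x Time, and baseline age, sex, skin-cancer history and perceived risk, each with its interaction with Time. A linear mixed model, or the planned ANOVA extended with these terms, would serve. Cohort year is optional.
- Show the unadjusted Group x Time result beside it.
- Stop reading the Group main effect as evidence of efficacy.
- Add a table of baseline characteristics by clinic.
- State that clinic-level, provider-level and unmeasured confounding remain, and word causal conclusions accordingly.

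The cost is SAP wording and a few degrees of freedom. No new data are needed, and fixing the covariates now avoids choosing them after the results are seen.
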